7.2.2. Columbia-Suicide Severity Rating Scale

The C-SSRS children's baseline/screening version assesses past and current suicidal ideations and behaviors to determine suicide risk and is administered at screening. The C-SSRS children's SLV scale is administered on day 1 (only for patients who completed Study SD-809-C-17) and weeks 2, 4, 8, 15, 28, 30, 34, 41, 54, and 55. Children 13 years of age and under may be interviewed separately or jointly with the caregiver/adult as appropriate or defined by the scale. For children over 13 years of age, caregiver/adult involvement is strongly encouraged. Questions should be directed to the child, but the caregiver/adult should be encouraged to add relevant information. The C-SSRS is administered through an interview by trained study personnel.

Suicidal ideation

- Patients with a positive C-SSRS suicidal ideation score on either items 1 or 2 or a change on the CDI-2 Parent or Self-Report Profiles consistent with increasing depressive symptoms must be 1) discussed with the medical monitor, 2) re-evaluated within 2 to 3 days in a clinic visit, and 3) treated according to the investigator's medical judgment. Consultation with a child and adolescent psychiatrist or licensed child/adolescent mental health provider is advised, followed by close ongoing monitoring.
- If patients endorse or report a C-SSRS suicidal ideation level of 3, 4, or 5, patients will be evaluated immediately by the study investigator and referred for psychiatric evaluation. The medical monitor will be immediately consulted. If it is determined by the investigator, after consultation with the medical monitor and the consulting psychiatrist, that exposure to the IMP may have contributed to this change in C-SSRS and/or increased depressive symptoms, IMP will be immediately discontinued and the patient terminated from the study. In cases where it is determined that IMP did not contribute to changes in depression or suicidality, the investigator will consult with the medical monitor, the consulting psychiatrist, and/or sponsor to determine whether the patient should continue in the study.

Suicidal behavior

- Actual attempt:
 - If patients report any suicidal behavior that is an actual attempt as assessed in the C-SSRS, they will be evaluated immediately by the study investigator, referred for psychiatric evaluation, and terminated from the study.
- Interrupted attempt, aborted attempt, or Preparatory Acts or Behavior:
 - If patients report any suicidal behavior that is interrupted, aborted, or preparatory as assessed in the C-SSRS, they will be evaluated immediately by the study investigator and referred for psychiatric evaluation. In cases where it is determined in the psychiatric evaluation that IMP did not contribute to changes in suicidal behavior, the investigator will consult with the medical monitor, the consulting psychiatrist, and/or sponsor to determine whether the patient should continue in the study.

A reference sample is provided in [Appendix E](#).

7.2.3. Children’s Depression Inventory, Second Edition, Parent and Self-Report Profiles

CDI-2 (Parent and Self-Report Profiles) is administered at screening and day 1 (only for patients who completed Study SD-809-C-17) and weeks 2, 4, 8, 15, 28, 30, 34, 41, 54, and 55. As the CDI-2 is designed for children 7 to 17 years of age, children 6 years of age on day 1 will not complete the Self-Report version; the caregiver/adult will complete the Parent version.

The CDI-2 Self-Report is a 28-item, self-report questionnaire assessing depressive symptoms in children 7 to 17 years of age with basic reading and comprehension skills. In the CDI-2, children are asked to choose 1 of 3 statements that most closely aligns with their feelings in the previous 2 weeks. The questionnaire covers both the major and minor symptoms of depression as outlined in the Diagnostic and Statistical Manual of Mental Disorders, Fourth Edition Text Revision ([Sun and Wang 2015](#)).

The CDI-2 Parent is a 17-item questionnaire administered to parents to assess depression-related behaviors observed in their children. In the CDI-2 Parent, parents are asked to rate their child’s behaviors in the past 2 weeks on a 4-point Likert scale from “not at all” to “much or most of the time”. The questionnaire allows for the division of depressive symptoms into functional problems and emotional problems ([Sun and Wang 2015](#)).

A reference sample is provided in [Appendix D](#).

7.3. Pregnancy

Any female patient becoming pregnant during the study will discontinue IMP.

All pregnancies of female patients participating in the study that occur during the study, or within 14 days after the end of the study, are to be reported immediately to the physician identified in the Clinical Study Personnel Contact Information section of this protocol, and the investigator must provide the sponsor (LSO/Syneos Health) with the completed pregnancy form.

The process for reporting a pregnancy is the same as that for reporting a serious adverse event but using the pregnancy form (see Section 7.1.5.3).

The investigator is not required to report patients who are found to be pregnant between screening and day 1, provided no IMP was given. All female patients who become pregnant will be monitored for the outcome of the pregnancy (including spontaneous, elective, or voluntary abortion). If the pregnancy continues to term, the outcome (health of the infant up to 8 weeks of age), including details of birth and presence or absence of any birth defect, congenital abnormalities, or maternal and newborn complications, will be reported to the sponsor. Any complication of pregnancy during the study and any complication of pregnancy that the investigator becomes aware of after withdrawal from the study will be reported as an adverse event or serious adverse event, as appropriate.

If the pregnancy in the female patient participating in the study does not continue to term, 1 of the following actions will be taken:

- For a spontaneous abortion, report as a serious adverse event.
- For an elective abortion due to developmental anomalies, report as a serious adverse event.
- For an elective abortion **not** due to developmental anomalies, report on the pregnancy form; do not report as an adverse event.

7.4. Medication Error and Special Situations Related to the Investigational Medicinal Product

Any administration of IMP that is not in accordance with the study protocol should be reported on the CRF either as a violation, if it meets the violation criteria specified in the protocol (Section 11.1.2), or as a deviation, in the patients source documents, regardless of whether or not an adverse event occurs as a result. All instances of incorrect medication administration should be categorized on the CRF as “Non-Compliance with IMP”.

The following are types of medication errors and special situations:

2. Medication error: Any unintentional error in the prescribing, dispensing, or administration of a medicinal product while in the control of the healthcare professional, patient, or consumer.
3. Overdose: Administration of a quantity of a medicinal product given per administration or cumulatively which is above the maximum recommended dose according to the authorized product information. Clinical judgment should always be applied. Any dose of IMP (whether the test IMP or placebo), whether taken intentionally or unintentionally, in excess of that prescribed must be immediately reported to the sponsor.
4. Misuse: Situations where the IMP is intentionally and inappropriately used not in accordance with the authorized product information.
5. Abuse: Persistent or sporadic, intentional excessive use of IMP which is accompanied by harmful physical or psychological effects.

6. Off-label use: Situations where an IMP is intentionally used for a medical purpose not in accordance with the authorized product information.
7. Occupational exposure: Exposure to an IMP, as a result of one's professional or non-professional occupation.
8. Breastfeeding: Suspected adverse reactions that occur in infants following exposure to a medicinal product from breast milk.

7.5. Clinical Laboratory Tests

All clinical laboratory test results outside of the reference range will be judged by the investigator as belonging to one of the following categories:

- abnormal and not clinically significant
- abnormal and clinically significant

The clinical significance of the laboratory values will be evaluated by the criteria described in the study laboratory manual and by the judgment of the investigator. A laboratory test result that is judged by the investigator as clinically significant will be recorded both on the source documentation and the CRF as an adverse event, and monitored as described in Section 7.1.2. An event may include a laboratory or diagnostic test abnormality (once confirmed by repeated testing) that results in the withdrawal of the patient from the study, the temporary or permanent cessation of administration of IMP or medical treatment, or further diagnostic work-up. Abnormal laboratory tests can be repeated without approval from the medical monitor. (Note: Abnormal laboratory or diagnostic test results at the screening visit that preclude a patient from entering the study or receiving IMP are not considered adverse events).

7.5.1. Serum Chemistry, Hematology, and Urinalysis

Clinical laboratory tests (eg, serum chemistry, hematology and urinalysis) will be performed at the time points detailed in Table 1. Clinical laboratory tests will be performed using the central laboratory. Specific laboratory tests to be performed are provided in Table 5.

Table 5: Clinical Laboratory Tests

Serum Chemistry	Hematology	Urinalysis
calcium	hemoglobin	protein
phosphate	hematocrit	glucose
sodium	red blood cell (RBC) count	ketones
potassium	mean cell volume	blood (hemoglobin)
chloride	platelet count	pH
creatinine	white blood cell (WBC) count, and differential count	specific gravity
glucose	– absolute neutrophil count (ANC)	microscopic
magnesium	– polymorphonuclear leukocytes (neutrophils)	– bacteria
blood urea nitrogen (BUN)	– lymphocytes	– RBCs
total cholesterol	– eosinophils	– WBCs
uric acid	– monocytes	– casts
alanine aminotransferase (ALT)	– basophils	– crystals
aspartate aminotransferase (AST)		
lactate dehydrogenase (LDH)		
alkaline phosphatase (ALP)		
bicarbonate or carbon dioxide		
total protein		
albumin		
total bilirubin		
direct bilirubin		

7.5.2. Other Clinical Laboratory Tests

7.5.2.1. Human Chorionic Gonadotropin Tests

Human chorionic gonadotropin tests in urine or serum will be performed for all females who are postmenarchal or ≥ 12 years of age as detailed in [Table 1](#) and if clinically indicated. Any female patient who becomes pregnant during the study will be withdrawn. Procedures for reporting the pregnancy are provided in [Section 7.3](#).

7.5.2.2. Urine Drug Screen

A UDS will be performed at the time points specified in [Table 1](#). A positive result for any of the specified drugs or their metabolites, without medical explanation, will preclude the patient from enrollment or continued participation in the study.

7.6. Vital Signs

Vital signs (BP, respiratory rate, body temperature, and pulse) will be measured at the time points detailed in [Table 1](#). All vital signs results outside of the reference ranges will be judged by the investigator as belonging to one of the following categories:

- abnormal and not clinically significant

- abnormal and clinically significant

Before BP and pulse are measured, the patient must rest in a supine or semi-erect/seated position and resting for at least 5 minutes. (The same position and arm should be used each time vital signs are measured for a given patient.)

For any abnormal vital sign finding, the measurement should be repeated as soon as possible. Any vital sign value that is judged by the investigator as clinically significant will be recorded both on the source documentation and the CRF as an adverse event, and monitored as described in Section 7.1.2.

On day 1 and weeks 4, 8, 28, and 54, orthostatic BP and pulse will be measured after the patient is in a standing position for at least 3 minutes.

7.7. Electrocardiography

A 12-lead ECG will be recorded at the time points detailed in Table 1. All ECGs will be performed after at least 5 minutes rest in a supine or semi-supine position. A qualified physician at a central diagnostic center will be interpreting the ECG.

All ECG results outside of the reference ranges will be judged by the investigator as belonging to one of the following categories:

- abnormal and not clinically significant
- abnormal and clinically significant

Any ECG finding that is judged by the investigator as clinically significant (except at the screening visit) will be considered an adverse event, recorded on the source documentation and in the CRF, and monitored as described in Section 7.1.2.

If a post-day 1 QTcF value >500 msec or change from baseline (Study TV50717-CNS-30046 or Study TV50717-CNS-30060) or day 1 (Study SD-809-C-17), as appropriate (see Section 9.7.2) >60 msec is found, the investigator should repeat the ECG assessment twice and compare the average of the 2 pre-treatment QTcF values (ie, the parent study baseline and screening values for patients rolling over from Study TV50717-CNS-30046 or Study TV50717-CNS-30060; or the day 1 and screening values from the current study for patient[s] who completed Study SD-809-C-17) to the average of the 3 post-day 1 QTcF values. The IMP must be stopped for any confirmed post-day 1 QTcF value >500 msec or increase from baseline (Study TV50717-CNS-30046 or Study TV50717-CNS-30060) or day 1 (Study SD-809-C-17) >60 msec.

7.8. Physical Examinations

Physical examinations, including height and weight, general appearance, skin, head, eyes, ears, nose, throat, neck, lymph nodes, cardiovascular, respiratory, musculoskeletal, abdominal, and extremities will be performed at the time points detailed in Table 1.

Weight must be measured with shoes and outerwear off.

Any physical examination finding that is judged by the investigator as clinically significant (except at the screening visit) will be considered an adverse event, recorded on the CRF, and monitored as described in Section 7.1.2.

7.9. Assessment of Suicidality

TEV-50717 is considered to be central nervous system (CNS)-active. In addition, there have been some reports of suicidal ideation or behavior as reported in the product label when it has been given to some patients with certain conditions. The sponsor considers it important to monitor for such events before and during this clinical study.

Some CNS-active IMPs may be associated with an increased risk of suicidal ideation or behavior when given to some patients with certain conditions. Although this IMP or other similar medicinal products in this class have not been shown to be associated with an increased risk of suicidal thinking or behavior when given to this study population, the sponsor considers it important to monitor for such events before or during this clinical study.

The study population being administered TEV-50717 should be monitored appropriately and observed closely for suicidal ideation and behavior or any other unusual changes in behavior. Consideration should be given to discontinuing TEV-50717 in participants who experience signs of suicidal ideation or behavior, and detailed recommendations are provided in Section 7.2.2.

The day 1 assessment of suicidal ideation and behavior and treatment-emergent suicidal ideation and behavior will be assessed during the study using the Children's C-SSRS described in Section 7.2.2.

Depression and Suicidality as an Adverse Event

Families and caregivers of patients will be instructed to monitor patients for any changes in or new onset of depressive symptoms; unusual changes in mood, cognition, or behavior; or onset of and/or changes in suicidal ideation or behavior, and to report such symptoms immediately to the study investigator. Telephone contacts and clinic visits also allow opportunities for investigators to assess adverse events.

If a relevant change in status is identified, patients will be seen immediately for an unscheduled visit by the study investigator and discussed with the medical monitor. The patient will be referred for further psychiatric evaluation if there is any suspected suicidal ideation with any level of intent, suicidal behavior, or clinical findings suggesting that the patient may be dangerous to self or others, and/or experiencing depression. The investigator will record these symptoms as an adverse event of depression and/or suicidality. If it is determined by the investigator, after consultation with the medical monitor and the consulting psychiatrist, that exposure to the IMP may have contributed to the adverse event of depression or suicidality, IMP will be immediately discontinued and the patient will be terminated from the study. Follow up with a pediatric psychiatrist or licensed child and adolescent mental health clinician will be arranged.

In cases where it is determined that IMP did not contribute to the adverse event of depression or suicidality, the investigator will consult with the medical monitor and/or sponsor to determine whether the patient should continue in the study.

A reference sample is provided in [Appendix E](#).

7.10. Neurological Examinations

Neurological examination, including mental status, cranial nerves, motor system (strength, tone, and posture), coordination, gait and balance, tendon reflexes, and sensation, will be performed at the time points detailed in [Table 1](#). Any neurological examination finding that is judged by the investigator as a potentially clinically significant change (worsening) compared with the screening value will be considered an adverse event, recorded on the CRF, and monitored as described in Section [7.1.2](#).

7.11. Concomitant Medication or Treatment

Concomitant therapy or medication usage will be monitored throughout the study. Parents/patients will be instructed during the course of the study to notify the investigator if any new medication is prescribed/administered, including over-the-counter medications. Any prescribed/administered medication should be reviewed with the investigator.

Medications that are allowed, provided that conditions outlined in the table are met, are shown in [Table 6](#). The tables for allowed and prohibited medications are not comprehensive and may not include all possible concomitant medications.

The medical monitor must be contacted if a patient is receiving (or has to begin or stop receiving during the study) a medication that is associated with QTc prolongation or that is a known strong CYP inhibitor, or if there are any questions regarding any medication not listed in [Appendix A](#).

Prohibited medications that are associated with QTc prolongation are listed in [Table 8](#), while prohibited antipsychotic drugs are listed in [Table 7](#).

7.12. Methods and Time Points of Assessing, Recording, and Analyzing Safety Data

All adverse events will be reviewed on a periodic basis by the CPP/medical monitor according to the safety monitoring plan (eg, scheduled safety reviews for TEV-50717) as preliminary safety databases become available.

Methods and time points of assessing safety data are discussed in Section [3.13](#). Procedures for recording safety data are discussed in Section [13.1](#), and methods of analyses are discussed in Section [9.7.2](#).

Information about the IDMC used for this study is provided in Section [3.7](#).

**8. ASSESSMENT OF
PHARMACOKINETICS/PHARMACODYNAMICS**

Pharmacokinetic and pharmacodynamic assessments will not be performed as part of Study TV50717-CNS-30047.

9. STATISTICS

This section describes the statistical analysis as foreseen at the time of planning the study. Changes, additions, and further details about the analyses will be described in the statistical analysis plan. After finalization of the statistical analysis plan, any additional analyses or changes to analyses that may be required will be fully disclosed in the clinical study report (CSR).

9.1. Sample Size and Power Considerations

This study is safety-oriented in nature; therefore, no formal hypothesis testing is planned for Part A. Based on the number of patients in the previous studies, up to approximately 227 patients (approximately 1 patient from the Phase 1b Study SD-809-C-17, up to approximately 99 patients from the Phase 2/3 Study TV50717-CNS-30046, and up to approximately 127 patients from the Phase 3 Study TV50717-CNS-30060) are estimated to enroll.

All patients who complete Study TV50717-CNS-30060 or Study TV50717-CNS-30046 are eligible to participate in Study TV50717-CNS-30047. As the number of patients to be randomized in parent Study TV50717-CNS-30046 has increased, the number of patients anticipated to be randomized into Study TV50717-CNS-30047 has also increased. The rationale for the increased sample size in Study TV50717-CNS-30046 is provided that protocol.

For the randomized drug withdrawal period, 190 patients to be included in the analysis will provide approximately 90% power to detect a difference between TEV-50717-treated and placebo-treated patients assuming a difference in YGTSS TTS of 4.5 with a standard deviation of 9 using a two-sided test for difference at a significance level of 0.05.

9.2. Analysis Sets

9.2.1. Intent-to-Treat Analysis Set

The intent-to-treat (ITT) analysis set will include all enrolled patients, regardless of whether or not a patient took any IMP. Enrolled subjects who are not randomized will be summarized separately as “Not randomized,” and randomized subjects will be analyzed based on their randomized treatment. A patient is considered enrolled according to the status reported in the database. All efficacy analyses will be based on the ITT analysis set.

9.2.2. Safety Analysis Set

The safety analysis set will include all patients who receive at least 1 dose of IMP.

The safety analysis set will be used for all safety analyses.

9.2.3. Randomized Withdrawal ITT Population

The Randomized Withdrawal ITT (RWITT) Population will include all patients enrolled in the randomized drug withdrawal period of the study.

9.2.4. Randomized Withdrawal Safety Population

The Randomized Withdrawal Safety (RWSAF) Population will include all patients enrolled in the randomized drug withdrawal period who are administered any study drug. All summaries of safety measures in the randomized withdrawal period will be summarized descriptively in the RWSAF Population.

9.2.5. Randomized Withdrawal Modified Intent-to-Treat Population

The Randomized Withdrawal Modified Intent-to-Treat (RWmITT) Population will include all patients enrolled in the randomized drug withdrawal period who receive study drug and have a YGTSS TTS at both the randomized drug withdrawal week 28 visit and the week 30 visit. Efficacy measures in the randomized drug withdrawal period will be analyzed as described in Section 9.5.3.1.

9.2.6. Responder Randomized Withdrawal Modified Intent-to-Treat Population

The Responder Randomized Withdrawal mITT (RRWmITT) Population will include all patients enrolled in the randomized drug withdrawal period who receive study drug and have a YGTSS TTS at both the week 28 visit and the week 30 visit and a $\geq 25\%$ reduction in the TTS from baseline in the parent protocol to week 28. Efficacy measures in the randomized drug withdrawal period will be analyzed as described in Section 9.5.3.1.

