When approximately 100 patients have completed the 28-week clinic visit, an interim analysis, including data from day 1 and up to week 28 visit only, will be conducted to provide descriptive, long-term safety and efficacy data to be used in regulatory submissions. To maintain data integrity of Study TV50717-CNS-30047, only a limited number of personnel who do not have contact with the sites will have access to this interim data in preparation for the regulatory filing. As no decisions regarding conduct of the study will be made based on the descriptive interim analysis, no alpha will be spent.

Patients who complete all scheduled visits will have procedures and assessments performed at the final visit (week 54). Patients who withdraw from the study before completing the week 54 evaluation period will have the week 54 procedures and assessments performed at their final visit, and a follow-up telephone contact for safety evaluation 2 weeks after their last dose of IMP.

The study schematic diagram is presented in [Figure 1](#). An additional diagram that details the blinded, randomized drug withdrawal/titration post-drug withdrawal period (Part B of the study) is presented in [Figure 2](#).

[figure not shown]
Figure 1: Overall Study Schematic Diagram

- ^a Maximum total daily dose for patients ≥ 40 kg is 48 mg/day (24 mg bid), 30 to <40 kg is 42 mg/day (21 mg bid), and 20 to <30 kg is 30 mg/day (15 mg bid). For those considered CYP2D6 impaired, maximum daily dose for patients ≥ 40 kg is 36 mg/day, 30 to <40 kg is 24 mg/day, and 20 to <30 kg is 18 mg/day (Table 2).
- ^b If a stable dose is reached before the indicated time, the patient should continue taking that dose for the remainder of the titration period and throughout the maintenance therapy dosing.
- ^c Dose adjustments may be made, as necessary, except for Part B.
- ^d See Figure 2.

Note: Screening visit is required only for patients rolling over from Study SD-809-C-17.
bid=twice daily; CYP=cytochrome P450; ET=early termination visit.

Figure 2: Study Schematic Diagram (Part B)

- ^a Ranges account for different dosing schedules for patients based on their previously established maintenance dose in Part A. Re-titration only applies to patients who were randomized to placebo during the withdrawal period.
- ^b Dose adjustments may be made, as necessary.

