3.6.2. Blinding and Unblinding

In case of a serious adverse event, pregnancy, or in cases when knowledge of the IMP assignment is needed to make treatment decisions, the investigator may unblind the patient's IMP assignment as deemed necessary, mainly in emergency situations. The patient's randomized treatment will be made available to the investigator(s) via the IRT system. If possible, the medical monitor should be notified of the event before breaking of the code. If this is not possible, the medical monitor should be notified immediately afterward, and the patient's randomized treatment should not be communicated to the medical monitor. Breaking of the randomization code can always be performed by the investigational center without prior approval by the medical monitor.

When a blind is broken, the patient will be withdrawn from the study, and the event will be recorded on the case report form (CRF). However, if a patient is unblinded by mistake, the

investigator should discuss with the medical monitor whether or not the patient should be withdrawn. The circumstances leading to the breaking of the code should be fully documented in the investigator's study files and in the patient's source documentation. Assignment of IMP should not be recorded in any study documents or source document.

In studies with blinding, for an adverse event defined as a suspected unexpected serious adverse reaction (SUSAR) (ie, reasonable possibility; see Section 7.1.4), Global Patient Safety and Pharmacovigilance may independently request that the blind code be broken (on a case-by-case basis) to comply with regulatory requirements. The report will be provided in an unblinded manner for regulatory submission. If this occurs, blinding will be maintained for the investigator and for other personnel involved in the conduct of the study and analysis and reporting of the data.

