9.3. Data Handling Conventions

For all variables, only the observed data from the patients will be used in the statistical analyses.

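### Every planned Part B efficacy analysis requires a week 30 tic score, so outcome-related dropout between weeks 28 and 30 can bias the only tested randomised comparison, and no planned efficacy analysis probes this

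*Protocol*

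**What the plan says.** The protocol fixes the following for Part B.

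- **Primary set (9.2.6, 9.5.3.1).** RRWmITT takes patients in the withdrawal period "who receive study drug and have a YGTSS TTS at both the week 28 visit and the week 30 visit" and who had at least a 25% TTS reduction from parent-study baseline to week 28.
- **Sensitivity sets (9.2.5, 9.5.3.1).** The same ANCOVA is repeated in RWmITT, which also needs TTS at weeks 28 and 30, and in the part of RRWmITT with at least a 35% reduction.
- **All-randomised set (9.2.3).** "The Randomized Withdrawal ITT (RWITT) Population will include all patients enrolled in the randomized drug withdrawal period of the study". Section 9.4 assigns Part B efficacy to RRWmITT or RWmITT, and no section assigns an efficacy analysis to RWITT.
- **Missing data (9.3).** For all variables, "only the observed data from the patients will be used in the statistical analyses".
- **General sentence (9.2.1).** "All efficacy analyses will be based on the ITT analysis set". Sections 9.4 and 9.5.3 confine the ITT set to open-label (Part A) efficacy.
- **Routes out of Part B.** Section 3.11 names lack of efficacy as a possible reason to stop. Section 3.6.2 states "When a blind is broken, the patient will be withdrawn from the study", with case-by-case discussion if the unblinding was a mistake.
- **Early-termination data.** Under Section 3.1, patients who withdraw early "will have the week 54 procedures and assessments performed at their final visit". Section 3.13.3.2.1 includes the YGTSS among those procedures. No section links that score to the week 30 endpoint.

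**The concern.** Membership of all three Part B efficacy analyses depends on something that happens after randomisation: having a TTS at week 30. Section 3.1.6 says that patients are randomised to check for return of symptoms. A patient who relapses and leaves before week 30 shows the outcome of interest, yet is excluded. If such exits differ between arms, the patients who remain are no longer comparable by randomisation.

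The responder rules do not have this problem. They use week 28 data, and blinded dosing starts on Day 197, so they restrict the population without breaking randomisation. Only the week 30 condition does that.

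At stake is the one comparison with inferential statistics (9.5), which supports the secondary objective on maintenance of effect (2.2.2). The sensitivity analyses share the exclusion, so they cannot show whether the result depends on it.

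**Working it through.** **1. The plan's own figure.** Section 9.1 says that "190 patients to be included in the analysis will provide approximately 90% power", "using a two-sided test for difference at a significance level of 0.05", for a difference of 4.5 and an SD of 9. Section 3.1.6 gives 2:1 allocation, so about 127 active and 63 placebo patients.

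- SE = 9 × √(1/63 + 1/127) = 1.387; 4.5/1.387 = 3.24.
- Power = 90.1% (normal approximation) or 89.8% (noncentral t). The stated figure reproduces.

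**2. Which patients each analysis keeps.**

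| Analysis | Week 30 TTS required? | Missing values restored? |
|---|---|---|
| Primary, RRWmITT | Yes (9.2.6) | No (9.3) |
| Sensitivity, RWmITT | Yes (9.2.5) | No (9.3) |
| Sensitivity, at least 35% subset of RRWmITT | Yes (inherited) | No (9.3) |
| RWITT | No (9.2.3) | No efficacy analysis assigned |

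Changing the set alone would not be enough. Under the observed-data rule, a week 28 to week 30 change still cannot be computed without a week 30 value.

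**3. Illustrations of direction and size.** The dropout rates and the dropouts' scores are assumptions, not figures from the protocol. The mean change is taken as +4.5 on placebo and 0 on active, with SD 9. For simplicity 127 and 63 are treated as the numbers before loss, although 190 in Section 9.1 is the number analysed. Dropouts are assumed to be 1 SD worse than their arm mean: +13.5 on placebo, +9 on active.

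- *3 of 63 placebo patients leave:* (4.5 × 63 − 13.5 × 3)/60 = 4.05, a fall of 10%. Power is 82.8% with 127 and 63 kept, or 81.5% with 127 and 60 (noncentral t).
- *6 of 63 placebo patients leave:* (4.5 × 63 − 13.5 × 6)/57 = 3.55, a fall of 21%. Power is 72.2% with 127 and 63 kept, or 69.2% with 127 and 57.
- *6 of 127 active patients leave, no placebo loss:* the retained active mean is (0 × 127 − 9 × 6)/121 = −0.45, so the difference rises to 4.5 + 0.45 = 4.95.
- *3 of 63 placebo and 6 of 127 active patients leave:* 4.05 + 0.45 = 4.50, so no bias.

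**4. A harsher assumption.** If the patients who leave are exactly the worst 5% or 10% of the placebo arm, the difference falls to 3.52 or 2.75. If they are the worst 5% or 10% of the active arm, it rises to 5.48 or 6.25. Completely random loss of 5% or 10% in both arms leaves it at 4.5 and lowers power only to 88.6% or 86.9% (normal approximation).

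The result therefore depends on who leaves and from which arm, which the protocol's figures do not settle.

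**The case against.** The strongest reply is that bias is possible but not shown. The randomised phase lasts two weeks, with a telephone contact at week 29, and placebo patients start re-titration straight after week 30, so few may leave. No Part B dropout rate is given, and equal selective loss in both arms leaves the difference unchanged. Relapse-driven loss on placebo is conservative. Part B serves a secondary objective; the primary one is long-term safety. All of this stands, and it limits the severity.

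Several stronger readings are tempting but not supported:

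- **That the comparison is biased by 10% to 21%.** Those figures come from chosen scenarios and are not expected effects.
- **That the protocol leaves the Part B analysis set in real contradiction.** The ITT sentence in 9.2.1 is too broad, but 9.4 and 9.5.3 confine ITT to Part A, and 9.5.3.1 names RRWmITT for Part B.
- **That differential loss would go unseen.** Section 9.4.1 summarises patients who enter and complete the withdrawal period, and withdrawals by reason. It also counts the other analysis sets, so RWITT is unused only for efficacy. These summaries could show differential loss, although presentation by arm is not spelled out, and they could not correct it.
- **That every unblinding removes a patient.** Sections 3.6.2 and 4.4 leave mistaken unblinding to discussion with the medical monitor.

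An unseen SAP may add detail. However, the sets, the primary analysis and the observed-data rule are fixed in the protocol, so the point does not rest on something left to the SAP.

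**Conclusion.** The concern holds as a structural weakness. All three Part B efficacy analyses condition on a post-randomisation value, nothing restores the missing patients, and the set that would keep them has no efficacy analysis. Outcome-related dropout between weeks 28 and 30 can bias the difference in either direction, depending on the arm affected, and no planned efficacy analysis tests this.

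The size is unknown. The illustrated range, from 3.55 to 4.95 around an assumed 4.5 when dropouts are 1 SD worse than their arm mean, rests on assumed dropout in one arm only; balanced selective loss gives 4.50. A reader might infer that the Part B result will be wrong, or that the design favours the drug. The protocol supports neither, and the route most natural to a withdrawal design, relapse on placebo, works against the drug. Severity: should-fix.

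**What to change.** 1. **9.2.6 and 9.5.3.1.** Make the primary Part B analysis all randomised patients (RWITT) who meet the 25% criterion at week 28, analysed as randomised, without requiring a week 30 TTS.
2. **Early-termination scores.** For patients who stop between Day 197 and week 30, use the early-termination YGTSS as the endpoint value. State that it may be an off-drug score, because Table 1 places that visit as soon as possible after the last dose; for a patient stopping active treatment this affects what is estimated.
3. **9.3.** Allow multiple imputation for endpoint values still missing in Part B. Add a delta-adjusted or tipping-point analysis that varies the assumed worsening of dropouts separately in each arm. Placebo-based imputation alone is not enough: filling in relapsed placebo patients from those who stayed leaves the bias described here largely in place.
4. **Supportive analyses.** Keep RRWmITT and RWmITT.
5. **9.2.1.** Limit the ITT sentence to Part A, to match 9.4 and 9.5.3.

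**Cost.** No new assessments, because the early-termination YGTSS is already scheduled, though some patients may not attend. The work is text in Sections 9.2, 9.3 and 9.5.3.1 and some programming. Changing the primary analysis set also needs a protocol amendment and the approvals described in Section 11.1.1, and should be settled before treatment codes are released.
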